In total there are four study visits. Participants will be assessed once by the study nurse at screening (the time of presentation in the ED), once by the study coordinator at baseline, and twice by the research assistant at 6 weeks post-randomization (at post-intervention), and 24 weeks post-randomization. Please see Table 1 for a complete measure administration schedule.

**Treatment allocation (F-SPS+UC or EUC):** Participants will be randomized to either receive the intervention, in addition to usual care (F-SPS+UC), or EUC only. They will be assigned in a 1:1 ratio of F-SPS+UC to EUC.

We will audio record F-SPS sessions if both the youth and the parent(s) or caregiver consent. These sessions will be reviewed by the principal investigators and the study staff in order to ensure fidelity to the treatment model.

In order to determine whether F-SPS+UC or EUC is related to a patient's health care service use, an analysis of participants' emergency room visits and unexpected medical appointments will also be conducted. OHIP numbers will be obtained at consent to link to ICES databases. .

We will recruit 128 adolescents to be randomized (64 adolescents per treatment arm) for this study (see 4.3 "Power Analysis").

**Intervention: F-SPS + UC (i)** is a manualized program that addresses the most common thoughts, feelings and conflicts that suicidal youth experience and teaches coping and safety skills to adolescents and their families. The program is the result of 3-years of development and quality improvement led by the PI ([name]), developed collaboratively with youth, families, and therapists. The program will be administered once weekly over 6 weeks by a trained therapist on an outpatient basis. Sessions consist of 1-hour spent one-to-one with the youth, followed by 1-hour with the youth and parent(s) or caregiver.

The therapist provides the youth and parent(s) or caregiver with a manual to use both during and between sessions. The program and manual address sources of conflict, ways to improve communication and ensure safety. The program resembles the only ED-based adolescent and family programs that have demonstrated effectiveness in decreasing suicidality. It is tailored to address the key concerns of the adolescent or family including mental health, academic problems, social or family conflict, acculturation issues, gender concerns or other stressors.

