## **DATA MANAGEMENT AND ANALYSIS**

**Outcomes:** This project will evaluate individual clinical outcomes, health care service utilization, client satisfaction, and implementation considerations; outcomes important to youth, family members, clinicians and policy-makers.

The *primary outcome measure* is change in Suicide Ideation Junior (SIQ-Jr) score. The SIQ-Jr is a youth-report measure of suicide risk behaviours that is valid, reliable, and sensitive to change and in accordance with youth preferences for self-administered mental health and SRB measures. The SIQ-Jr has 15 items, is reliable and valid in 12-18 year olds, and has been used in clinical trials, providing known effect sizes for sample size calculations.

*Secondary outcomes* include measures that are also feasible, reliable, valid and sensitive to change. These include:

(2a) Mental illness symptom severity, including those of depression, anxiety, substance use, psychosis, affective lability, and disruptive behaviour, as reported by youth and parents and measured by the Youth Self-Report, Life Problems Inventory, and Children's Behaviour Checklist); (2b) functional impairment, as assessed by the Columbia Impairment Screen (youth and parent report); (2c) family communication, assessed by the Conflict Behaviour Questionnaire (youth and parent report); (2d) cost-effectiveness analysis (CEA) of the incremental costs of the F-SPS as compared with UC in reducing SIQ-Jr score; and The frequency of ED and unscheduled (crisis) health appointments, using a health and social services diary and ICES databases, will be used to assess the effect of the F-SPS intervention on acute mental health crises. (2e) fidelity to the F-SPS intervention (implementation outcome) will employ a self-report measure to be developed by the project team. Measurement of treatment fidelity is key to understanding clinical and system level outcomes because an intervention cannot be effective unless it is appropriately implemented in the care pathway and developed with fidelity.

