### **Power Analysis and Data Analytic Plan**

The sample size calculation is based on the assessment of between-group difference in change in SIQ-Jr score. This is a superiority study in which the implementation of the F-SPS intervention should only be recommended for study in a larger, multi-centre sample if the change in the primary outcome is significantly greater than in the control group. Two controlled clinical trials of an ED based intervention for suicidal youth have reported effect sizes of 0.4 for suicide attempt and 0.95 for suicidal ideation as measured by the SIQ-JR^23. A sample size of 128 participants provides 80% power ( $p=0.05$ ; 2-tailed t-test) to detect an effect size  $\geq 0.5$ , (based on a standard deviation [SD] of 14 and smallest clinically important difference of 7).

The principle of intent-to-treat will be applied to the analysis of outcomes. *H1*: The primary outcome SIQ-Jr will be compared between arms using repeated measures ANOCOVA with the corresponding baseline measure as the covariate. Mean differences and corresponding confidence intervals will be calculated. A two-sided, p-level of 0.05 will be applied for the primary outcome. *H2*: The number of unscheduled hospital visits will be compared between arms using a Poisson model. The two-sided level for the secondary outcomes will be adjusted (Bonferroni) to account for multiple testing. Implementation outcomes (i.e., fidelity to the intervention protocols) will inform client outcomes. Analysis of implementation data will be descriptive (fidelity to implementation of F-SPS model in both sites), and associative (statistical association of clinician fidelity to F-SPS and patient outcomes).

**Feasibility.** The ED at SickKids manages more adolescents with acute mental health presentations than any other hospital in the Toronto Central LHIN (TC-LHIN), on average 842 per year, (we estimate more than half for SRB). Sick Kids also has a strong history of successfully conducting ED-based RCTs and has

an established research infrastructure for identification and recruitment of potential research participants (Pediatric Research Academic Initiative at SickKids Emergency [PRAISE]). In addition, through our previous development work including an open pilot in the Urgent Care (Crisis) Clinic, several therapists at our centre are familiar with the intervention and have experience using it with acutely suicidal youth and families.

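### Optional improvement: Holm's step-down could replace plain Bonferroni for the secondary outcomes, with the same family-wise error control and a small to moderate gain in power

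*Protocol*

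**What the plan says.** The protocol's section Power Analysis and Data Analytic Plan separates the two levels of testing. For the primary outcome: "A two-sided, p-level of 0.05 will be applied for the primary outcome". For the rest: "The two-sided level for the secondary outcomes will be adjusted (Bonferroni) to account for multiple testing". Bonferroni is the only method named, and neither the number of tests nor a per-test level is given.

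The sample size rests on the primary outcome alone: "The sample size calculation is based on the assessment of between-group difference in change in SIQ-Jr score". It is justified by "A sample size of 128 participants provides 80% power", "based on a standard deviation [SD] of 14 and smallest clinically important difference of 7", and the Procedure section gives 64 per arm with 1:1 allocation. No power is promised for any secondary outcome.

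The Outcomes paragraph under Data Management and Analysis lists the secondary scales. Symptoms (2a) are "measured by the Youth Self-Report, Life Problems Inventory" and the Child Behavior Checklist. The Columbia Impairment Scale (2b) and the Conflict Behavior Questionnaire (2c) follow, each by youth and parent report. The same paragraph adds the count of emergency and unscheduled visits. The Children's Affective Lability Scale is not among the instruments named there, but the Measures section puts it with the parent-completed secondary measures, and Table 1 schedules it at baseline, week 6 and week 24.

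**The concern.** Plain Bonferroni holds every test in the family at 0.05/m, however many of the other tests have already succeeded. Holm starts at the same 0.05/m for the smallest p-value and, after each rejection, relaxes the threshold to 0.05/(m−1), 0.05/(m−2) and so on. Its family-wise guarantee is the same and, like Bonferroni's, needs no assumption about correlation. Everything Bonferroni rejects, Holm rejects too.

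The secondary outcomes are related child and parent reports of symptoms, functioning and family conflict, and the programme addresses several of these together. An effective programme could well move more than one of them, and that is the setting in which Holm gains. At stake is the chance of confirming the second, third and later secondary effects once a first has been established.

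**Working it through.** **Inputs from the protocol.** 64 per arm; SD 14; difference 7; so d = 7/14 = 0.5; two-sided 0.05.

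**Assumptions, because the protocol does not give them.**
- One test per scale. The Outcomes paragraph gives 3 (symptoms) + 2 (impairment) + 2 (conflict) + 1 (visits) = 8 tests; adding the Children's Affective Lability Scale makes 9.
- Equal correlation of 0.3 to 0.5 between outcomes.
- True effects of d = 0.5 or d = 0.3.
- The visit count, which the protocol analyses with a Poisson model, is represented by a normal test statistic like the others.

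**Step 1: reproduce the plan's own figure.** In the normal approximation, power = Φ(d√(n/2) − z). With d√(n/2) = 0.5 × √32 = 2.83 and z = 1.96, power is 0.807. The exact t-test gives 0.801 and needs 63.8, rounded up to 64 per arm. The stated 128 and 80% are confirmed.

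**Step 2: power of a single test at the Bonferroni level.**
- m = 8: 0.05/8 = 0.00625; at d = 0.5 power is 0.537 (normal) or 0.521 (t).
- m = 9: 0.05/9 = 0.00556; power is 0.522 (normal) or 0.505 (t).
- Over a wider range of m = 5 to 12, power runs from 0.60 to 0.49 (normal) or from 0.59 to 0.47 (t).

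These figures follow from the family size and n. Holm's first step uses the same level, so they do not measure the difference between the two methods.

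**Step 3: Bonferroni against Holm.** Test statistics were simulated as correlated normals (200,000 replicates per scenario). Bonferroni rejects every p ≤ 0.05/m. Holm goes through the ordered p-values with thresholds 0.05/m, 0.05/(m−1), …, 0.05 and stops at the first failure. Average power per true effect at d = 0.5, over correlations 0.3 and 0.5:

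| Effects that are real | m = 8: Bonferroni → Holm | m = 9: Bonferroni → Holm | Gain |
|---|---|---|---|
| 1 | 54% → 54% | 52% → 52% | about 0 points |
| 3 | 54% → 56% | 52% → 54% | about 2 points |
| 4 | 54% → 57% | 52% → 55% | about 3 points |
| 6 | 54% → 60% | 52% → 57% | 5 to 6 points |
| all | 54% → 65% | 52% → 63–64% | about 11 points |

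At d = 0.3 the starting power is 14 to 15%. The gain is 1 to 2 points with six effects real and 2 to 3 points with all real.

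**Step 4: what stays the same.** The probability of at least one rejection was identical under the two methods in every scenario, because both need the smallest p-value to fall below 0.05/m. In the scenarios with at least one null outcome, family-wise error stayed below 0.05 for both (checked at correlations 0 and 0.5).

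**The case against.** The strongest reply is that nothing here is wrong. Bonferroni is valid, prespecified and conservative, and it controls the error the protocol sets out to control. No secondary power is promised, and progression to a larger multi-centre study is tied to the primary outcome, which is untouched. All of this stands, and it is why the point is optional.

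Three stronger readings are tempting and are not supported.

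- **Power is given away for nothing.** Bonferroni provides one fixed threshold and directly matching simultaneous intervals at level 1 − 0.05/m, which Holm does not readily give. That advantage is real but modest here: the protocol mentions confidence intervals alongside the primary comparison and does not promise simultaneous ones for secondary outcomes.
- **Bonferroni causes the roughly 50% power per secondary test.** Step 2 shows that this comes from eight or nine tests with 64 per arm. Holm helps only after another secondary outcome has passed. If the visit count (the second stated hypothesis) were the only real effect, the change would do almost nothing for it.
- **The protocol is deficient because it does not itemise the family.** The list of tests is detail that a statistical analysis plan commonly supplies, and none is shown here. The Narrative Summary names mental health crises among the primary outcomes while the analysis sections treat visits as secondary. That is a separate question, which arises equally under either method.

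**Conclusion.** The point holds as an optional efficiency improvement, not as a defect. Holm gives the same family-wise guarantee and never fewer rejections. The gain in average power per true effect runs from about 0 to about 11 points at d = 0.5, and is about 3 points at most at d = 0.3. The upper end requires every secondary effect to be real and as large as the effect planned for the primary; with about half of them real, 3 points is a fair expectation.

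That Holm never rejects less is a mathematical property and needs no assumption. The size of the gain rests on the assumed family of eight or nine tests, the correlations, the effect sizes and the normal treatment of the visit count, none of which the protocol fixes.

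**What to change.** In Power Analysis and Data Analytic Plan, in the sentence on the level for secondary outcomes, replace the bracketed word Bonferroni with: Holm step-down, family-wise two-sided 0.05. Make the change before unblinding.

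The cost is a few words in one sentence, with no effect on sample size, the primary analysis or data collection. The one drawback is in reporting: simultaneous confidence intervals that match Holm decisions are less simple to present than Bonferroni intervals. If the sponsor values those intervals for the secondary outcomes, keeping Bonferroni is a defensible choice.

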### **Privacy and Confidentiality**

The confidentiality of clinical trial participants will be maintained. Participants will be assigned a unique study ID number. Information collected from participants will be de-identified, entered and stored in the REDCap external research database that is supported by SickKids research IT. Consent forms will be stored separately from registry data in a research folder that will be stored in a locked cabinet in a locked research office. Information linking identifying information to the registry ID will be stored separately in a password protected electronic file on a SickKids computer, only accessible to the PI and research team.

**Data destruction and retention:** Following completion of the study, the data will be kept as long as required then securely destroyed as required by SickKids policy. Hard copy documents will be shredded and disposed of in a secure manner. Electronic documents will be deleted securely.

